4.5.3.4 Crossover (Stage 2)

- Patients randomized to CM with progressive disease or no response after one cycle of CM may cross over to receive ACM.
- Patients randomized to CM with a best response of PR after 2 cycles of CM may also cross over to receive ACM.

- Continued use of mitoxantrone is optional after completion of one cycle of ACM
- Mitoxantrone must be omitted from subsequent cycles if the patient's lifetime daunorubicin equivalent exceeds 460 mg/m² (see *Appendix G* for conversion table) or the left ventricular ejection fraction (LVEF) drops below 45%. Patients crossing over who meet the above criteria will receive only AC (alvocidib and cytarabine) for all cycles instead of ACM.
- Patients who cross over to ACM may receive up to a combined total (CM + ACM) of 4 cycles.

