PBSC	Peripheral Blood Stem Cells
PFS	Progression-Free Survival
PH	Proportional Hazards (model)

* The term CRp appears in this document to maintain compatibility with the study's case report forms, however CRp will not be used by the hematologists performing the central review of patients' responses and it is not expected to be used by the investigators.

PR	Partial Remission
PT	(MedDRA) Preferred Term
RFS	Relapse-Free Survival
ROC	Receiver Operating Characteristic (curve)
SAE	Serious Adverse Event
SAP	Statistical Analysis Plan
SCT	Stem Cell Transplant/Transplantation
SMQ	Standardized MedDRA Query
SOC	(MedDRA) System Organ Class
TEAE	Treatment Emergent Adverse Event
TLS	Tumor Lysis Syndrome
WHO	World Health Organization

3. Definitions

Standard statistical terminology (e.g., type-1 error rate and significance level) is omitted intentionally. Efficacy endpoints are defined in Section 4.1 below (see Table 1).

Baseline Value: last measured value prior to the first dose of study drug (or prior to randomization for patients not treated)

Combined CR: response assessment of CR, CRi or CRp

Combined Remission: response assessment of CR, CRi, CRp or PR

Crossover Patient: a patient randomized to CM who, following 1-2 cycles of CM, receives ACM as stipulated in the study protocol

Cycle 1: period of time from the first dose of study drug until the start of study drug in cycle 2 or the start of alternative AML therapy other than supportive measures such as blood product transfusions (hence a patient whose first response assessment in cycle 1 is a CRi or CRp is considered to have achieved CR if neutrophils and platelets recover prior to initiation of cycle 2 or alternative AML therapy)

Cycle-1 Combined CR Rate: percentage of patients who achieve a combined CR (CR, CRi or CRp) after one cycle of treatment

Cycle-1 Combined Remission Rate: percentage of patients who achieve a combined remission (CR, CRi, CRp or PR) after one cycle of treatment

Cycle-1 CR Rate: percentage of patients who achieve a CR after one cycle of treatment (see section 7.9.1)

Intent-to-Treat Population: all patients randomized to receive study drug regardless of whether they actually received study drug and regardless of whether evidence is found indicating they failed to meet study inclusion/exclusion criteria or had other protocol violations (see section 7.1)

Neutrophil Recovery: Absolute neutrophil count $\geq 1 \times 10^9/L$ following the administration of study drug

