7.1. Analysis Populations

The intent-to-treat (ITT) patient population includes all patients randomized to receive study drug regardless of whether they actually received study drug and regardless of whether evidence is found indicating they failed to meet study inclusion/exclusion criteria or had other protocol violations. When the ITT patient population is analyzed, patients are grouped according to their randomized treatment regardless of actual treatment received. The ITT patient population is the analysis population for the primary analyses of efficacy endpoints (i.e., all statistical inference and tests of hypotheses related to efficacy endpoints in stage 2 and univariate summaries of efficacy endpoints in stage 1 and the exploratory study arms).

The safety patient population is the subset of ITT patients who received at least one dose of study drug. When the safety patient population is analyzed, patients are grouped according to actual treatment received. ACM is considered a patient’s “treatment received” in the safety patient population if alvocidib is administered at any time during the study (except for ACM administered to a “crossover” patient). The safety patient population is the analysis population for all analyses of safety data.

The response-available patient population is the subset of safety patients who have at least one response assessment on study. However, patients are excluded from the response-available patient population if they have an important protocol deviation, such as when evidence is found indicating they failed to meet any study inclusion/exclusion criterion. When the response-available patient population is analyzed, patients are grouped according to actual treatment received. ACM is considered a patient’s “treatment received” in the response-available patient population if alvocidib is administered at any time prior to a combined remission or at any time during the study for patients never achieving combined remission (except for ACM administered to a “crossover” patient). The response-available population is used for biomarker analyses and sensitivity (secondary, supportive) analyses of efficacy endpoints.

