7.5.2. Type-1 Error Rate Control for Multiple Comparisons

Without taking appropriate measures, testing multiple efficacy parameters inflates the overall significance level since the probability of making a type-1 error in at least one from a set of hypothesis tests is greater than the probability of making a type-1 error in any single test. The hierarchical closed test procedure^{3,4} will be used to maintain the overall 2.5% significance level.

The order of efficacy endpoints for the hierarchical closed test procedure is:

1. Cycle-1 CR rate
2. Progression-Free Survival
3. Stem Cell Transplant Rate
4. Cycle-1 Combined CR Rate
5. Cycle-1 Combined Remission Rate
6. Overall Survival
7. Combined Remission Duration
8. Combined CR Duration
9. CR Duration

The final analysis will be conducted at a one-sided 2.378% significance level using the statistical procedures described below. Cycle-1 CR rate, the primary efficacy endpoint, will be declared statistically significant if its test p-value ≤ 0.02378 . A secondary efficacy endpoint will be declared statistically significant only if its test p-value ≤ 0.02378 and all efficacy endpoints preceding it in the hierarchy are statistically significant. In other words, declaration of statistical significance for efficacy endpoints will advance in order down the hierarchy only until a p-value > 0.02378 is found.

In addition, although primary and supportive analytical methods are specified for each endpoint in the hierarchy, only the p-value from the primary analysis will be used for deciding statistical significance. Supportive (sensitivity) analyses are to demonstrate the robustness of primary results to slight modifications to how endpoints are defined and/or analyzed.

Declarations of statistical significance will not be advanced for endpoints not included in the hierarchy of the closed test procedure (e.g., ECOG performance status).

It is worthwhile noting...

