7.9.1. Remission Rates

The primary efficacy endpoint is cycle-1 CR rate (i.e., the percentage of patients who achieve a CR after one cycle of treatment). Cycle 1 does not end until the patient starts cycle 2 or alternative AML therapy other than supportive measures (e.g., blood product transfusions). Therefore, a patient whose first response assessment in cycle 1 is a CRi or CRp* is considered to have achieved CR if neutrophils and platelets recover prior to initiation of cycle 2 or alternative AML therapy including bone marrow or stem cell transplant. Patients who, for any reason, do not supply bone marrow for response assessment are counted among those not achieving remission. Best response during the study (i.e., best response following one or more cycles of treatment) was not selected as the primary efficacy endpoint due to the anticipated confounding effects of patients who are randomized to CM but crossover after one or two cycles to receive treatment with ACM.

Three response assessments are planned for each postbaseline bone marrow sample:

1. The "central review" performed by a panel of independent, expert hematologists according to an approved charter under change control

* See footnote on page 6.

2. The “local review” of bone marrow and blood test results by the investigator at the study center where patient is enrolled
3. The “sponsor review” by employees and/or agents of Tolero Pharmaceuticals

It is beyond the scope of this SAP to restate or summarize the written charter detailing the methods and criteria the panel of hematologists use to grade response, but both central and local assessments are made according to criteria specified in the study protocol. The primary assessments of remission for comparing efficacy across treatment arms is the central review of bone marrow; however, in cases where the central hematologists are unable to rate response, the investigator’s response assessment will be used in place of the missing central assessment. Supportive efficacy analyses will be conducted using assessments from the local and sponsor reviews.

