7.9.2. Progression-Free Survival

PFS time is defined for all patients and is measured from the date of randomization (Day 1) until (a) treatment failure, (b) relapse after combined remission, or (c) death from any cause, whichever occurs first.

Treatment failure is defined as failing to achieve a combined remission following induction therapy. The date of treatment failure is the protocol-specified date for bone marrow collection following the first induction attempt (i.e., at neutrophil and platelet recovery or Day 45 of the treatment cycle, whichever occurs first), regardless of whether the patient received a second induction attempt (unless the second induction resulted in a combined remission in which case “treatment failure” does not apply).

Additional rules for defining PFS time are:

- A patient found to have relapsed after missing one or more scheduled response assessments will have his PFS time end on the scheduled date for the first missed response assessment following the last confirmation of combined remission
- A patient who misses the first scheduled response assessment and who never achieves combined remission will have his PFS time end on the scheduled date for the first response assessment (unless the patient died before this date)

Rules for censoring PFS time are:

- A patient with PFS continuing as of the date he is lost to follow-up will have his PFS time censored on the date of his last response assessment
- A patient with PFS continuing as of the database lock will have his PFS time censored on the date of his last response assessment

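### SAP 7.9.2 cancels treatment failure after a second-induction remission and is silent on crossover, so on a plain reading remissions on ACM erase CM failures and pull PFS toward no difference

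*SAP*

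**What the plan says.** SAP 7.9.2 states: "Treatment failure is defined as failing to achieve a combined remission following induction therapy". The event is dated at the scheduled marrow after the first induction (count recovery or Day 45), "regardless of whether the patient received a second induction attempt (unless the second induction resulted in a combined remission". In that case treatment failure is declared not to apply. The regimen of the second induction is not specified.

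Protocol 4.5.3.4 opens crossover to first-cycle failures: "Patients randomized to CM with progressive disease or no response after one cycle of CM may cross over to receive ACM". Protocol 4.5.3.3 separately lets non-responders continue induction with the Medical Monitor's permission and no grade 4 toxicity.

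In the ITT analysis (SAP 7.1), "patients are grouped according to their randomized treatment regardless of actual treatment received". The SAP's per-protocol population also excepts ACM given at crossover, so these patients stay in CM there too.

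SAP Section 3 defines a crossover patient as "a patient randomized to CM who, following 1-2 cycles of CM, receives ACM as stipulated in the study protocol". SAP 7.9.1 rejects best response as the primary endpoint because of the "anticipated confounding effects of patients who are randomized to CM but crossover after one or two cycles". SAP 7.9.2 does not mention crossover, and Table 6 varies only transplant censoring.

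The hierarchy in SAP 7.5.2 has nine endpoints and lists "2. Progression-Free Survival" directly after the primary.

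**The concern.** A CM patient with no response after cycle 1 has had the event that PFS is meant to record. If that patient crosses over, remits on ACM, and the crossover cycle counts as the second induction, the event is removed retrospectively. The time then gained is credited to CM. Whether a CM failure counts thus depends on a later response to the other arm's drug. The clause covers both arms, but only CM patients can be rescued by the other arm's regimen.

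The better ACM works as rescue, the longer PFS becomes on CM, and the hazard ratio moves toward 1. No planned sensitivity analysis would show this. Under the SAP's order, a non-significant PFS stops testing of the seven endpoints below it. The SAP saw this confounding when it chose the primary endpoint, but 7.9.2 leaves it open.

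**Working it through.** **1. The plan's own figures.** The documents give no power, event count or effect size for PFS, so the check starts from the CR sample sizes. With unpooled variance, n per arm = (z₀.₉₇₅ + z₀.₉₀)² × [p₁(1−p₁) + p₂(1−p₂)] / (p₁−p₂)².

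- SAP 5.1.2, 70% vs 40%: 10.507 × 0.45 / 0.09 = 52.5. With the O'Brien-Fleming look at 56 of 106, the drift is 3.2554, and 3.2554² × 0.45 / 0.09 = 52.99 per arm. N is 105.97, rounded up to 106, with boundary p-values 0.00321 and 0.02378, as in SAP Tables 3 and 4.
- Protocol 11.2.2, 70% vs 30%: 10.507 × 0.42 / 0.16 = 27.6, rounded up to 28 per arm.

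**2. CM failures erased.** Expected number = n × (1 − CM remission rate) × crossover uptake × rescue rate on ACM. Uptake and rescue are assumptions.

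| Uptake / rescue | 53 per arm, CM 40% | 28 per arm, CM 30% |
|---|---|---|
| 50% / 30% | 53 × 0.6 × 0.15 = 4.8 | 28 × 0.7 × 0.15 = 2.9 |
| 70% / 40% | 53 × 0.6 × 0.28 = 8.9 | 28 × 0.7 × 0.28 = 5.5 |
| 80% / 50% | 53 × 0.6 × 0.40 = 12.7 | 28 × 0.7 × 0.40 = 7.8 |

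**3. Effect on PFS, by simulation.** Assumptions, none from the documents except the rates, sample sizes and alphas:

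- the planning CR rates stand in for combined remission;
- failures are events at Day 45;
- remitters relapse or die at Day 45 plus an exponential time (median 9 months, both arms);
- rescued patients do so at Day 95 plus the same exponential;
- censoring at 2 years, unstratified log-rank test.

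At 53 per arm, 70% vs 40%, one-sided 2.378%:

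| Rule | HR, no ACM rescue | Power, no ACM rescue | Power, 15% of ACM failures also rescued |
|---|---|---|---|
| Failure fixed at cycle 1, both arms | 0.63 | 48% | 48% (rescue has no effect) |
| As written, 50% / 30% | 0.75 | 23% | 34% |
| As written, 70% / 40% | 0.86 | 12% | 14% |
| As written, 80% / 50% | 0.98 | 3% | 7% |

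Repeat runs move these powers by about 2 points. At the protocol's 28 per arm, 70% vs 30% and one-sided 2.5%, power falls from about 52% to between 25% and 6% over the same three cells, with no ACM rescue.

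A second model (censoring uniform over 6–24 months, rescued remission from month 3, median remission 6 to 12 months) gives 47–60% with failure fixed against 21–31% as written, for 50%/30% at 53 per arm.

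**4. A one-sided repair.** Suppose cancellation were kept only for a second cycle of the randomised regimen. Take identical cycle-1 remission (40%) and duration in both arms, 53 per arm, nominal one-sided 2.378%, and no CM failure rescued by more CM. If 10%, 20% or 30% of ACM failures remit on a second ACM cycle, the false-positive rate is about 6%, 16% or 27%.

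**The case against.** **The term is undefined.** The protocol treats continued induction (4.5.3.3) and crossover (4.5.3.4) under separate headings, and the SAP uses its crossover term elsewhere when it means crossover. Limiting a second induction attempt to continued treatment on the assigned regimen is therefore tenable. This stands: a reader might infer that the SAP certainly cancels CM failures after crossover, but the text does not settle it. The wider reading is still the plainer one, because no regimen is named and the protocol's exploratory objective asks whether ACM can induce CR after CM has failed. Two programmers could derive different PFS dates, so a rule is needed either way.

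**The current protocol differs.** The SAP is written to Amendment 7. The supplied protocol describes Amendment 11, has no PFS, and ranks EFS fifth of six with no cancellation clause. A reader might infer that most secondary endpoints are at risk of being blocked. That holds only under the SAP's order; in the protocol only transplant rate lies below EFS. EFS still counts treatment failure without saying how crossover affects it.

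**The direction is conservative and the primary is safe.** Both are true. Cycle-1 CR closes when cycle 2 starts, and the bias runs against ACM. Even with failure fixed at cycle 1, PFS power is only about 48% under these assumptions, so the gate would fail about half the time anyway.

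**Treatment policy.** It can be argued that ITT should follow the whole strategy. OS already does that; an endpoint that counts treatment failure should record failure of the assigned regimen.

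**Conclusion.** The concern holds as a should-fix. SAP 7.9.2 leaves crossover unaddressed, and on its plain reading a remission obtained on ACM removes a CM failure and biases PFS toward no difference. The direction follows from the rules. The sizes (power from about 48% to between 23% and 3% at 53 per arm, somewhat less loss if ACM failures are also rescued) rest on assumed uptake, rescue and remission duration.

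Three stronger readings are not supported:

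- A reader might infer that rescued CM patients count as event-free. They lose only the failure event; later relapse or death still counts, in the CM arm.
- A reader might infer that crossover is the usual second induction on CM. No document gives its uptake.
- A reader might infer a risk of a false claim for ACM. On this reading the present rule works against ACM; a one-sided repair would create that risk.

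Patients who cross over with a PR after two CM cycles are already in combined remission, so the clause does not touch them.

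**What to change.** - **Primary PFS.** Delete the cancellation clause for both arms. A patient not in combined remission at the cycle-1 response assessment has a PFS event on that date, whatever induction or crossover therapy follows. Align the 7.9.2 rule for a missed first assessment, which also turns on never achieving combined remission.
- **Supportive PFS.** Report the version with cancellation and state whether crossover ACM counts as a second induction.
- **Do not** keep cancellation only for the randomised regimen. That favours ACM and can inflate type I error (step 4).
- **Duration and RFS endpoints.** Do not credit the CM arm with remissions first obtained after crossover.
- **Reconciliation.** Apply the same rule to treatment failure in the protocol's EFS when the Amendment 7 SAP is brought into line with the current protocol, before database lock.

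The cost is a few lines in the SAP and one supportive analysis, with no extra patients; the SAP already plans a crossover population, so these patients must be identified anyway. The downside is that a patient of either arm who remits only on a second induction counts as a PFS event at cycle 1.

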4.5.3.2 Stage 2: Treatment with ACM or CM

Patients enrolled in Stage 2 will be randomized to either ACM or CM and will receive treatment as outlined below:

Stage 2: Randomized to ACM: Treatment with ACM over Days 1-9

Follow the Stage 1 treatment schema above

Stage 2: Randomized to CM: Treatment with CM over Days 1-4

- **Days 1, 2, and 3: cytarabine (C) - Continuous over 72 hours**
2 gm/m² by continuous IV infusion over 72 hours (± 2.5 hours)
(ie, 667 mg/m² daily for total of 2 gm/m²)
- **Day 4: mitoxantrone hydrochloride (M) is administered 12 hours after completion of cytarabine treatment**
40 mg/m² by IV infusion over 1-2 hours (± 10 minutes)

4.5.3.3 Evaluation After Cycle 1

- Patients who achieve CR, CRi, CRp, or PR after the first cycle (completion of all doses) may receive up to 3 additional optional cycles of treatment.
 - After completing the first cycle of treatment, continued use of mitoxantrone is optional.
 - Mitoxantrone must be omitted from subsequent cycles if the patient's lifetime daunorubicin equivalent exceeds 460 mg/m² (see *Appendix G* for conversion table) or the left ventricular ejection fraction (LVEF) drops below 45%.
- Patients not demonstrating evidence of CR, CRi, CRp, or PR after the first cycle of treatment will be considered for removal from the study, although with permission of the Medical Monitor, induction treatment may continue if clinically indicated and provided there is no evidence of toxicity \geq NCI CTCAE grade 4.
- Perform the End of Study Assessments for those patients who do not continue on study to receive at least one additional cycle of treatment (see *Section 5.5*).

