5.4.4 Cycle 1 – At Hematologic Recovery

- Assess response by bone marrow biopsy and/or aspiration at time of hematologic recovery (ie, absolute neutrophil count (ANC) >1000 μ L and platelet count >100,000 μ L) or Day 45 (\pm 2), whichever occurs first. If the bone marrow biopsy and/or aspirate is nonproductive or not diagnostic, the procedure must be repeated within 7 days.
 - At time of response assessment, 6 to 8 bone marrow slides will be prepared and sent to the Sponsor. Details regarding the collection and shipping of these slides is provided in the Study Manual.
- Assess for AEs, including tumor lysis clinical symptoms
- Record only those medications (prescription, nonprescription, nutritional supplements) administered in conjunction with an AE.

5.4.5 Cycles 2 - 4

Patients who achieve CR, CRi, CRp, or PR after the first cycle (completion of all doses) may receive up to 3 additional optional cycles of treatment. After completing the first cycle of treatment, continued use of mitoxantrone is optional. Mitoxantrone must be omitted from subsequent cycles if the patient's lifetime daunorubicin equivalent exceeds 460 mg/m² (see *Appendix G* for conversion table) or the LVEF drops below 45%.

Patients not demonstrating evidence of CR, CRi, CRp, or PR after the first cycle of treatment will be considered for removal from the study, although with permission of the Medical Monitor, induction treatment may continue if clinically indicated and provided there is no evidence of toxicity \geq NCI CTCAE grade 4.

However, patients randomized to CM with progressive disease or no response after 1 cycle of CM may cross over to receive ACM. In addition, patients randomized to CM with the best response of a PR after 2 cycles of CM may also cross over to receive ACM. Patients who cross over to ACM may receive up to a combined total (CM + ACM) of 4 cycles.

There is a maximum limit of 90 days between the start of cycles unless otherwise discussed with the medical monitor.

5.4.5.1 Cycles 2 - 4, Day 1 – Within 10 Hours Prior to First Dose

Perform the following assessments in patients receiving subsequent cycles of chemotherapy:

- *If clinically indicated*, administer pretreatment IV hydration, oral allopurinol, and oral phosphate binder (see *Section 4.6.1*)

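### The SAP's rule of censoring event-free patients at the last response assessment, on its most natural (marrow) reading, makes censoring depend on later outcome and lowers late PFS, RFS and CR-duration estimates

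*SAP*

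**What the plan says.** **Censoring.** SAP 7.9.2 states: "A patient with PFS continuing as of the database lock will have his PFS time censored on the date of his last response assessment". Patients lost to follow-up get the same date. SAP 7.9.5 (RFS) and 7.9.6 (CR duration) repeat the rule. Only OS (SAP 7.9.4) uses a wider date, the last assessment of any type.

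**Meaning of the term.** SAP section 3 does not define a response assessment. SAP 7.9.1 says: "Three response assessments are planned for each postbaseline bone marrow sample". SAP 7.9.2 says: "The date of treatment failure is the protocol-specified date for bone marrow collection following the first induction attempt". A patient who misses the first assessment and never remits "will have his PFS time end on the scheduled date for the first response assessment".

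**Events.** PFS and RFS count relapse and any death, with no limit relative to the last marrow. CR duration counts relapse only and censors a death in remission at the date of death. SAP section 7 takes relapse and death dates from the clinical database.

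**Schedule.** Protocol 5.4.4: "Assess response by bone marrow biopsy and/or aspiration at time of hematologic recovery", or at Day 45 if that comes first. Up to four cycles are allowed, and Protocol 5.4.5 adds: "There is a maximum limit of 90 days between the start of cycles unless otherwise discussed with the medical monitor". Protocol 4.5.3.3: "Perform the End of Study Assessments for those patients who do not continue on study to receive at least one additional cycle of treatment". The end-of-study visit (Protocol 5.5) includes a marrow unless one was done in the preceding 30 days. After that, Protocol 5.6 schedules only telephone calls, to month 24, covering death, transplant, relapse and continued remission.

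**The concern.** Kaplan-Meier and log-rank methods require that a patient's censoring time carry no information about the later outcome. Suppose two patients have the same last marrow. One relapses at month 20 and is followed to month 20. The other is reported in remission at month 24 and is censored at the last marrow, months earlier. Good outcomes leave the risk set early, poor outcomes stay in it, and the curve is pulled down.

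The extreme case is a one-cycle responder who goes off study within 30 days of the remission marrow and stays in remission to month 24: RFS and CR duration are censored on Day 1. SAP 7.9.1 also lets a patient first rated CRi be "considered to have achieved CR if neutrophils and platelets recover prior to initiation of cycle 2 or alternative AML therapy". If that happens on blood counts alone, the last marrow precedes the CR date and the censored time is not positive.

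At stake are the milestone percentages that SAP 7.9.2, 7.9.5 and 7.9.6 call for (6, 12 and 18 months are the examples given), the RFS and CR-duration medians, and the PFS test, which is step 2 of the SAP hierarchy. The remission durations are steps 7 to 9. RFS is in no hierarchy.

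**Working it through.** The documents give no event count, hazard ratio or power for these endpoints, so there is no stated figure to reproduce. The size is an illustration.

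**Inputs from the documents.** Cycle marrow at Day 45. Cycle starts at most 90 days apart, so marrows at Days 45, 135, 225 and 315 (45 + 3 × 90), or 1.478, 4.435, 7.392 and 10.349 months at 365.25/12 days per month. Follow-up to month 24.

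**Assumptions.** 60% remission. Non-remitters fail at Day 45. Remission is exponential with median 10 months. Patients have 1, 2, 3 or 4 cycles with equal probability, and no end-of-study marrow is added.

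**True PFS.** G(t) = 0.6 × 2^(−(t − 1.478)/10).
- G(12) = 0.6 × 2^(−1.052) = 0.289
- G(18) = 0.6 × 2^(−1.652) = 0.191
- G(24) = 0.6 × 2^(−2.252) = 0.126

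**PFS under the marrow reading.** The 12.6% who are event-free at month 24 are removed at their last marrow, a quarter at each date. Let c be the share already removed. Between marrow dates a and b the Kaplan-Meier curve is multiplied by (G(b) − c)/(G(a) − c).

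| Interval (months) | c | Factor |
|---|---|---|
| 1.478 to 4.435 | 0.0315 | (0.4888 − 0.0315)/(0.6000 − 0.0315) = 0.804 |
| 4.435 to 7.392 | 0.0630 | (0.3982 − 0.0630)/(0.4888 − 0.0630) = 0.787 |
| 7.392 to 10.349 | 0.0945 | (0.3244 − 0.0945)/(0.3982 − 0.0945) = 0.757 |
| 10.349 to 12 | 0.1259 | (0.2893 − 0.1259)/(0.3244 − 0.1259) = 0.823 |
| 10.349 to 18 | 0.1259 | (0.1909 − 0.1259)/(0.3244 − 0.1259) = 0.327 |

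- 12 months: 0.6 × 0.804 × 0.787 × 0.757 × 0.823 = 0.237, against 0.289
- 18 months: 0.6 × 0.804 × 0.787 × 0.757 × 0.327 = 0.094, against 0.191

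After Day 315 every patient left in the risk set has an event by month 24, so the curve falls to zero although 12.6% are event-free.

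**RFS, limiting case.** If the CR marrow is the last marrow, the rule estimates P(T > t given T ≤ 22.5 months), because 24 − 1.48 = 22.5. With S(12) = 0.435, S(18) = 0.287 and S(22.5) = 0.210:
- 12 months: (0.435 − 0.210)/0.790 = 0.285, against 0.435
- 18 months: (0.287 − 0.210)/0.790 = 0.097, against 0.287

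**Simulated ranges** over last-marrow schedules (1 to 2 cycles, 1 to 4 cycles, uniform spreads, and an added end-of-study marrow), with a 10-month median:

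| Quantity | Last-contact censoring | Marrow reading |
|---|---|---|
| PFS at 12 / 18 months | 29 / 19% | 21–25 / 8–10% |
| RFS at 12 / 18 months | 44 / 29% | 30–35 / 10–12% |
| RFS median (months) | 10 | 7.6–8.9 |
| CR duration at 12 / 18 months (20% of remissions end in death) | 51 / 37% | 38–44 / 16–19% |
| CR-duration median (months) | 12.5 | 9.1–10.6 |

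The PFS median barely moves (4.1 against 3.8–4.1 months).

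**PFS log-rank test, 53 per arm, one-sided 2.5%, simulated, illustrative only.**
- 70% vs 40% remission, medians 12 vs 8 months: power 85% with last-contact censoring, 73% under the marrow reading.
- 70% vs 40%, equal 10-month medians: 49% and 51%.
- No difference, equal cycle counts: type I error 2.6% and 2.8%.

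These runs ignore the SAP 7.9.2 provision that a successful second induction cancels treatment failure, and they use 2.5% where the SAP's final level is 2.378%.

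**The case against.** **The marrow reading is not certain.** SAP 7.9.1 says how many reviews each marrow gets, not that only marrow can be a response assessment. It also lets blood counts upgrade CRi to CR. Protocol 5.6 calls the telephone contacts follow-up assessments, and Protocol 4.1 lists even OS and EFS among response assessments. If a report of continued remission counts, the bias disappears. This stands, and makes the point conditional. The wider wording kept for OS alone, and the marrow-based treatment-failure date, still make marrow the more natural reading. Two programmers could reach different results.

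**The back-dating rule for missed assessments might restore balance.** It does not. It needs a missed scheduled assessment, and on the marrow reading none is scheduled during telephone follow-up.

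**The versions differ.** SAP section 4 names Amendment 7, whereas the supplied protocol describes Amendment 11 (section 2.7). The Amendment 7 schedule cannot be checked. This stands.

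**The power figures are fragile.** This stands. If crossover ACM counted as a second induction and rescued 40% of CM failures (both assumptions), the 85% and 73% become about 27% and 11%. The loss remains, but the levels cannot be relied on.

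**Stronger readings that a reader might infer.** One is that the PFS test has an inflated type I error. That needs last-marrow timing to differ by arm. If ACM patients had 2–4 cycles and CM patients 1–2, error would be about 5%; with CM having more cycles it would fall to about 2%. No document predicts either. Another is that the current protocol's EFS carries the same bias. It is censored at 2 years, and nothing ties it to the last marrow; it only lacks a rule for earlier censoring dates.

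**Conclusion.** The point holds conditionally. On the most natural reading of an undefined term, the SAP censors by outcome, and late Kaplan-Meier percentages and the RFS and CR-duration medians are too low. With a 10-month median remission the PFS shortfall is about 5 points at 12 months (28.9 − 23.7) and 10 at 18 months (19.1 − 9.4). It is smaller for shorter remissions and larger for longer ones: with an 18-month median, true PFS of 40% and 32% becomes 27–35% and 12–16%. All remission rates, durations and cycle counts are assumptions.

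The PFS test loses power only if remissions last longer in one arm. Type I error is essentially unchanged when cycle counts are equal. The primary endpoint, cycle-1 CR, is unaffected. PFS, RFS and CR duration appear in the SAP but not among the current protocol's endpoints. It should be fixed, but it is not critical.

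**What to change.** - In SAP 7.9.2, 7.9.5 and 7.9.6, define response assessment, and censor event-free patients at the last contact of any kind, clinic or telephone, that documents the patient alive and without relapse.
- If a 24-month limit is used, measure it from randomization and apply it to events and censoring alike.
- Keep last-marrow censoring only as a sensitivity analysis, with events found after the last marrow also removed. It then says nothing beyond the last marrow.
- Write the same date rule for EFS when the SAP is aligned to the current protocol.

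A simulated check of the main rule, with the protocol's call schedule and 10% random loss to follow-up, returned PFS of 28.9% and 19.1% at 12 and 18 months, equal to the true values.

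The cost is SAP wording, since the supplied protocol already collects the telephone data. The downside is that remission reported by telephone is less rigorous than remission confirmed by marrow.
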